7.3.2. Immunogenicity

Missing immunogenicity data will be retained as missing.

7.4. Visit Windows

There will be no derivation for visit windows in terms of summary of assessments. Nominal visits will be used for listings and tables.

7.5. Analysis Windows for Immunogenicity

Immunogenicity results will be excluded if the study day collected occurs outside of the analysis windows, as indicated in [Table 3](#).

Table 3: Immunogenicity Analysis Windows

Scheduled Visit	Analysis Target Study Day	Analysis Window	Analysis Window	
			Lower Bound	Upper Bound
Day 28	29	± 5 days	24	34
Day 180	181	± 14 days	167	195
Day 365	366	± 21 days	345	387

7.6. Unscheduled Visits

Data collected at unscheduled visits will be included in listings but not included in summaries. Unscheduled visits may be included in shift tables when specified.

7.7. Subgroups

Subgroup analysis will be completed by age subgroup analyses category (age 60-69, age 70-85, age 70-79, age 80-85, and age 60-75 [at randomization]) and baseline tertiles (RSV-A, RSV-B, hMPV-A and hMPV-B NAbs and RSV and hMPV IgG prefusion F protein-specific antibody titers), where specified.

Additional subgroup analyses may be requested on an as-needed basis.

This document is confidential.

8. Demographics, Other Baseline Characteristics and Medication

Demographics, Other Baseline Characteristics and Medication will be presented separately for the main trial and observational extension trial.

8.1. Main Trial Demographics, Other Baseline Characteristics and Medication

8.1.1. Subject Disposition and Withdrawals

Subject disposition will be presented for all enrolled subjects, which will include the following:

- The number of subjects enrolled (i.e., provided informed consent and provided demographic and/or baseline screening assessments);
- The number of subjects resulting in screen failure;
- The number of subjects screened but not randomized;
- The number of subjects randomized.

Among the randomized subjects, the following will be summarized by vaccine groups and aggregate IVX-A12 and Overall:

- The number of subjects randomized by age stratification category
- The number (%) of subjects in Safety Set;
- The number (%) of subjects in Full Analysis Set and Per Protocol Set;
- The number (%) of subjects who completed the main trial;
- The number (%) of subjects who continue to observational extension trial;
- The number (%) of subjects who prematurely discontinued from the trial and the associated reasons.

All disposition will also be listed. Listings of inclusion in analysis sets and exclusion reasons will also be presented.

A summary of screen failures will be presented, which will include the number (%) of subjects resulting in screen failure and their reason for not being eligible. Also, for the screen failures who do not meet eligibility criteria, the inclusion or exclusion criteria not being met will be presented.

A list of protocol deviations will be provided with the date the deviation occurs, the category (eg, inclusion/exclusion criteria, informed consent (ICF)/subject privacy, etc.), severity (major/minor) and the description of the deviation. Major and minor protocol deviations will be summarized separately in the same table by vaccine group, IVX-A12 aggregate, and overall for the Randomized Set.

8.1.2. Demographic and Baseline Characteristics

Demographics and other baseline characteristics will be summarized for the Full Analysis Set by vaccine group, IVX-A12 aggregate, and overall. Descriptive statistics for height, weight, and body mass index (BMI) will be presented including n, mean, SD, median, minimum, and maximum for numeric variables and frequency and percentage for categorical variables.

This document is confidential.

Demographics and baseline characteristics will include age (descriptive statistics and categorically by age subgroup analyses categories: 60 to 69 years, 70 to 85 years, 70-79 years, 80-85 years, 60-75 years, gender, race, ethnicity, Dalhousie Clinical Frailty Score, height, weight, body mass index). Collected age (at time of randomization) will be used in table.

Height (in cm) at baseline = height (in inches) * 2.54

Weight (in kg) at baseline = weight (in lbs) * 0.4536

BMI (kg/m²) at baseline = Weight(kg)/[Height(cm)*0.01]²

Baseline RSV-A (IU/mL, MN50 titer), RSV-B (IU/mL, MN50 titer), hMPV-A, hMPV-B titers, and their corresponding tertiles will be presented including n, geometric mean, median, minimum and maximum.

Demographics and baseline characteristics will be repeated for the Safety Set and Per Protocol Set.

Demographics and baseline characteristics will also be repeated by age subgroup analyses categories for the Safety Set and Per Protocol Set.

Eligibility, including Inclusion/exclusion criteria, demography, baseline characteristics, smoking and alcohol use history, household information will be listed.

8.1.3. Medical History and Concomitant Diseases

Medical and surgical history will be summarized by primary System Organ Class (SOC) and Preferred Term (PT) coded via Medical Dictionary for Regulatory Activities (MedDRA) version 26.0 or greater. The number and percentage of subjects will be displayed for each SOC and PT for the Safety Set by vaccine group, IVX-A12 aggregate, and overall. Summaries will be ordered by descending frequency of SOC, and then within a SOC, by overall descending frequency of PT in the total column. If a subject has one or more history events more than once, the subject is counted only once under any given SOC or PT.

All medical history data of subjects will be listed for the Safety Set.

8.1.4. Vaccine History

All non-trial vaccines that were received within the past one year will be summarized by vaccine names. The number and percentage of subjects will be displayed for each vaccine name for the Safety Set by vaccine group, overall IVX-A12 aggregate, and overall. Number of subjects with at least one vaccine received within the past one year resulting in a reaction will also be summarized.

All vaccine history data of subjects will be listed for the Safety Set.

8.1.5. Medication

All medications will be coded using the World Health Organization Drug Dictionary (WHO-DD) Format B3 Version March 2023.

Prior medications are defined as any medications taken before trial dose administration, regardless of whether it was stopped prior to the trial dose administration. Concomitant medications are defined as any medications with start date or stop date on or after the trial dose administration until the end of the main trial. The prior and concomitant medications will be summarized separately.

This document is confidential.

For the purposes of classifying medications into prior/concomitant, the algorithms in [section 7.3.1](#) will be used for imputing missing dates.

Medications will be summarized by Anatomical Therapeutic Chemical (ATC) Level 4 and PT. If ATC Level 4 is missing, the next higher non-missing ATC Level will be used. For each medication, the number and percentage of subjects will be displayed for the Safety Set by vaccine group, IVX-A12 aggregate, and overall. The tables will be sorted by overall descending frequency of ATC Level 4 and then, within an ATC Level, by overall descending frequency of PT in the total column. If a subject has one or more medications more than once, the subject is counted only once under any given ATC Level 4 or PT.

All prior and concomitant medications, up to the end of the main trial, will be listed for the Safety Set.

8.1.6. Extent of Exposure

All subjects are planned to receive either a) 1 dose of IVX-A12 at two dose levels, with or without MF59® adjuvant, or b) 1 dose of placebo. The doses are administered at Day 0 (Study Day 1). Dose administration data will be summarized and analyzed for the Safety Set, by vaccine group, IVX-A12 aggregate, and overall.

The number and percentage of subjects who received vaccination will be summarized. The frequency and percentage of administration route, body location, and laterality for each vaccination will be displayed as well.

A listing will be provided for the Safety Set.

8.2. Observational Extension Trial Demographics, Other Baseline Characteristics and Medication

A listing of subject disposition, including study discontinuation reason, will be provided for all subjects who continue into the observational extension trial (EES).

No baseline characteristics, protocol deviations, medical history or medication data will be provided.

This document is confidential.

9. Immunogenicity

9.1. Main Trial Immunogenicity

The immunogenicity analyses will be performed on the PPS, unless otherwise stated. Immunogenicity results will be excluded if the study day collected occurs outside of the analysis windows as indicated in [Table 3](#).

All data will be listed, for the FAS, until the end of the main trial.

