13.1.1 Analysis Sets

Safety Set: The safety set will consist of all subjects who received a dose of IVX-A12 or placebo. Subjects will be analyzed as treated.

Full Analysis Set (FAS): The FAS will include all randomized subjects who received a dose of IVX-A12 or placebo. Subjects will be analyzed as randomized.

Per-Protocol Set (PPS): The PPS will include all subjects in the FAS who received a dose of IVX-A12 or placebo and have no major protocol deviations that have a significant impact on immunogenicity results. Subjects will be analyzed as randomized.

Extension Enrolled Set: The Extension Enrolled Set will consist of all subjects who consented to participate in the extension portion of the trial. Subjects will be analyzed as initially treated.

13.1.2 Analysis of Disposition, Demographics, Other Baseline Characteristics, Medical History and Medications

Subject disposition will be summarized for all enrolled subjects which will include the number of subjects enrolled, screen failed, and randomized. For subjects who are randomized, the number and percentage of subjects in each of the analysis sets will be summarized by treatment group.

Demographics (age, gender, race) and other baseline characteristics (including baseline RSV and hMPV NAb titers) will be summarized descriptively by treatment group for all randomized subjects.

Medical and surgical history will be summarized by primary SOC and PT and by vaccine group. All medical history data will be listed.

All prior and concomitant medications will be summarized by Anatomical Therapeutic Chemical Level 4 and PT and by treatment group. All medications will be listed.

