6.1.4. Full Analysis Set

The Full Analysis Set (FAS) will include all randomized subjects and received a dose of IVX-A12 or placebo. Subjects will be analyzed according to randomized group. This set will be used for analysis of demographics and other baseline characteristics and subject listings for immunogenicity.

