6.1.5. Per Protocol Set

The Per Protocol Sets (PPS) will include all subjects in the FAS who received a dose of IVX-A12 or placebo and have no major protocol deviations, which may exclude subjects from PPS. Subjects will be analyzed according to randomized group. If a subject has a major protocol deviation or RSV/hMPV infection after Day 28, their post-Day 28 data point may be excluded. Blinded data review meeting (BDRM) will be conducted prior to each Interim Analysis and prior to data base lock and unblinding of the vaccine groups. During the BDRMs, a final decision (sponsor call) will be taken as to which subjects/visit will be excluded.

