6.3. Protocol Deviations

Protocol deviations are defined as instances in which subjects or investigational site study personnel fail to adhere to the protocol requirements (e.g., eligibility criteria, addition or deletion of tests, dosing, duration of treatment, and/or any other aspect of the study design) and the deviation is considered major if the deviation has the potential to impact subject safety or the primary and secondary endpoints of the trial. Deviations are collected in Clinical Trial Management System (CTMS).

This document is confidential.

7. General Aspects for Statistical Analysis

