To identify unknown RSV or hMPV infections, boxplots will be produced for serum anti-RSV/A-, RSV/B-, hMPV/A- and hMPV/B-specific NAb to display the fold-rise from Day 28 to Day 180, Day 28 to Day 365, and Day 180 to Day 365. The box plots will be produced for the PPS and will utilize log2 transformed fold-rise and back-transformed. Listings will also be generated for serum anti-RSV/A-, RSV/B-, hMPV/A- and hMPV/B-specific NAb, where fold increase ≥ 8 , from Day 28 to Day 180, Day 28 to Day 365, and Day 180 to Day 365. The listings will be produced for the FAS.

CCI

This document is confidential.

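### All immunogenicity estimates use the PPS, whose exclusion grounds are wider in the SAP than in the protocol, and no comparison is repeated on the FAS

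*SAP*

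**What the plan says.** **Analysis set.** SAP 9.1 says: "The immunogenicity analyses will be performed on the PPS, unless otherwise stated". The readable text of section 9 names the FAS for two immunogenicity outputs, both listings. One is the general listing in 9.1 ("All data will be listed, for the FAS, until the end of the main trial"). The other is the listing of rises of 8-fold or more in 9.1.2 ("The listings will be produced for the FAS"). SAP 6.1.4 describes the role of the FAS in the same way: "This set will be used for analysis of demographics and other baseline characteristics and subject listings for immunogenicity". Part of section 9.1 after 9.1.2 is blacked out and is not judged here.

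**PPS membership.** Protocol 13.1.1 admits FAS subjects who "have no major protocol deviations that have a significant impact on immunogenicity results". SAP 6.1.5 admits those who "have no major protocol deviations, which may exclude subjects from PPS". SAP 6.3 defines the key word: "the deviation is considered major if the deviation has the potential to impact subject safety or the primary and secondary endpoints of the trial". SAP 6.1.5 also allows a post-Day 28 data point to be left out after a major deviation or an RSV/hMPV infection. It assigns the decision as follows: "During the BDRMs, a final decision (sponsor call) will be taken as to which subjects/visit will be excluded".

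**Declared changes.** SAP section 12 lists the added gender factor, the age subgroups, the dropped extension analysis and an added LRTI table and listing. It does not mention the PPS criterion.

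**The concern.** A per-protocol main analysis is customary for vaccine immunogenicity, and the protocol names no set for it, so choosing the PPS contradicts nothing. The difficulty is that it stands alone. Exclusions made after randomisation can unbalance the arms, and the usual way to see whether they matter is to repeat the comparison on everyone randomised and dosed. That comparison is not planned.

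The SAP also widens the grounds for exclusion. Protocol 9.1.3 gives failure to collect Day 0 samples for serology or for safety as an example of a major deviation. A missed safety sample says nothing about titers. It would not meet the protocol's PPS criterion, but the SAP wording allows it to exclude a subject.

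At stake are the pairwise GMT and GMFR comparisons in SAP 9.1.1.1, which are meant to assess whether an adjuvant is needed and how each active arm differs from placebo, and the SRR contrasts in 9.1.1.2. The Day 180 and Day 365 persistence results are also exposed, through the infection rule.

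**Working it through.** **1. The two PPS definitions compared**

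| Item | Protocol 13.1.1 | SAP 6.1.5 and 6.3 |
|---|---|---|
| Ground for exclusion | Major deviation with significant impact on immunogenicity | Major deviation; no impact criterion |
| Meaning of major | Not defined there | Potential to affect safety, or primary or secondary endpoints |
| Infection after Day 28 | Not mentioned | Data point may be left out |
| Group | As randomised | As randomised |
| Decision | Not stated there | Sponsor, at blinded data review meetings |

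The SAP's grounds are wider, so the resulting set can only be the same size or smaller. The protocol synopsis carries a phrase close to the SAP's, apparently struck through, next to the newer criterion, and the version history records an updated PPS definition. The SAP may simply have kept superseded wording; that is an inference.

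**2. The plan's own figure.** SAP 4.3.1 and protocol 13.4 claim more than 90% power for a 2-fold GMT difference, with SD 0.5 log10 and two-sided 0.05.

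Power = Φ(δ/SE − 1.96), with δ = log10(2) = 0.301 and SE = 0.5 × √(1/n1 + 1/n2).

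- 100 v 100: SE = 0.0707, giving Φ(2.30) = 98.9%.
- 100 v 50: SE = 0.0866, giving Φ(1.52) = 93.5%.

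The GMT claim reproduces.

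**3. Loss of precision.** Assume equal exclusion in all arms (no rate is given):

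| Excluded | A12a v A12d | Active v placebo |
|---|---|---|
| 5% | 98.6% | 92.3% |
| 10% | 98.1% | 91.0% |
| 15% | 97.5% | 89.3% |

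Loss of subjects is not the main problem.

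**4. Possible bias.** Let a fraction f of one arm be excluded, with mean log10 titer lower by d than in those kept. The FAS mean is then the PPS mean minus f × d, so PPS GMT / FAS GMT = 10^(f × d). Both f and d are assumptions; d = 0.5 equals the planning SD.

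- f = 0.05, d = 0.25: 10^0.0125 = 1.029
- f = 0.10, d = 0.5: 10^0.05 = 1.122
- f = 0.15, d = 0.5: 10^0.075 = 1.189

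These are shifts in one arm. For a contrast the shift is 10^(f1·d1 − f2·d2), which is 1 when both arms lose similar subjects at similar rates.

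For SRR, if 10% of one arm is excluded, all of them non-responders, and the true rate is 50%, the PPS rate is 0.50/0.90 = 55.6%, which is 5.6 points too high.

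**5. Scale.** The 95% half-width of a GMT ratio is 10^(1.96 × SE): about 1.38-fold for 100 v 100 and 1.48-fold for 100 v 50. Even the largest shift above (1.19-fold) is smaller than either, and well below the 2-fold design difference.

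**The case against.** The strongest reply is that the safeguards are real and the trial is descriptive. This largely stands, and it rules out several stronger readings.

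- **That no result respects the randomisation.** Not supported. SAP 6.1.5 analyses PPS subjects by randomised group and settles exclusions at blinded meetings before each interim analysis and before lock.
- **That the FAS serves only for listings.** This is true for immunogenicity only. SAP 6.1.4 and 8.1.2 also use it for demographics and baseline characteristics.
- **That selection cannot be examined at all.** Not supported. SAP 8.1.1 plans numbers in each set by group, listings of exclusion reasons, and major deviations by group on the Randomized Set. SAP 8.1.2 gives baseline characteristics, including neutralising titers, for both FAS and PPS. These show who was left out and why, but they do not show what the contrast would be with them included.
- **That safety-only deviations automatically exclude a subject.** The SAP says they may.
- **That infected subjects are removed and boosting is hidden.** The rule concerns post-Day 28 data points, so it cannot touch the Day 28 endpoints. SAP 9.1.2 plans boxplots and FAS listings to find unrecognised infections. Titers that include infections mix vaccine persistence with natural boosting, so preferring them as the main result would change the question asked.
- **That the choice of formulation depends on this analysis.** Protocol 4.4 (version 5.0, April 2024) reports that A12a was already chosen, and the SAP refers to an event of October 2024.

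One qualification concerns blinding. SAP 4.4 unblinds the clinical research associates and the clinical lead at the end of each Day 365 visit, before lock. The SAP does not say whether they take part in the final review. The Day 28 exclusions settled before the first interim analysis are unaffected.

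**Conclusion.** The point holds in a limited form. In the readable text, every immunogenicity estimate and contrast comes from the PPS and none is repeated on the FAS. The SAP's exclusion grounds are wider than the protocol's, and section 12 does not say so.

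The risk is modest, given analysis as randomised, blinded decisions and reported exclusions. The actual bias cannot be computed, because the documents give neither an exclusion rate nor titers for excluded subjects. A reader might take 3% to 19% as the expected bias in the comparisons. It is not: it is the shift in one arm under assumed values, and similar exclusions in the other arm would largely cancel it. The point is worth correcting because the comparisons in SAP 9.1.1.1 carry confidence intervals and are used to judge the need for adjuvant, and because the check is nearly free.

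**What to change.** 1. In SAP 6.1.5, restore the protocol criterion: only major deviations judged to have a significant impact on immunogenicity exclude a subject. If exclusions have already been settled under the wider wording and the data are unblinded, do not reopen them; state in section 12 which rule was applied.
2. Add a sensitivity analysis that repeats the Day 28 GMT, GMFR and SRR contrasts (A12a v A12d, and each v placebo) on the FAS with available titers, as randomised. State whether the Table 3 windows apply.
3. Show Day 180 and Day 365 GMTs on the FAS without infection exclusions, labelled as a sensitivity analysis beside the PPS result, with a note that they combine vaccine persistence and natural boosting.

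The cost is a wording change, one further run of existing programs with a different population flag, and a few more tables. FAS titers are already to be listed, so no new data are needed. If this is added after unblinding, section 12 should say so, as it already does for the LRTI table that was added late.

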9.1.1. Primary Immunogenicity Endpoints and Analyses

The primary immunogenicity endpoints are listed in [section 5.1.1.2](#). The definition of geometric mean titer (GMT) and geometric mean fold rise (GMFR) are provided in [section 7.1](#).

9.1.1.1. Analysis for Primary Immunogenicity Endpoint

The unadjusted GMT of RSV/A RSV/B-, hMPV/A-, and hMPV/B-specific NAb (live-virus assays) at Day 28 will be calculated with their 95% CIs (unadjusted) by vaccine group, aggregate IVX-A12, and overall. The GMT of RSV and hMPV IgG prefusion F protein-specific antibody titers (ELISAs) at Day 28 will also be provided. Quartiles, minimum and maximum of the NAb will also be displayed.

The unadjusted geometric mean fold rise (GMFR) at Day 28 versus baseline (Day 0) of (in serum anti-RSV/A-, RSV/B-, hMPV/A-, and hMPV/B-specific NAb ([live-virus assays]) and RSV and hMPV IgG prefusion F protein-specific antibody titers ([ELISAs]), and the ratios will be calculated at Day 28 with their 95% CI for PPS by vaccine group, aggregate IVX-A12, and overall. A complete case analysis will be performed whereby those subjects in the PPS with Day 28 data are included. 95% CIs (unadjusted) will be calculated by back transformation of the 95% CI for the mean of the log2 transformed individual fold rise computed using Student's t distribution. Quartiles, minimum and maximum of the fold-rise in antibody titer from baseline (Day 0) to Day 28 will also be displayed.

Using an ANCOVA, the adjusted GMTs and GMFRs at Day 28 and its 95% CI will be calculated. The outcome variable is Day 28 log2 transformed titers. The factors will include vaccine group, age stratification category, and gender and the covariates will include, log2 transformed baseline titers. Least square means and 95% CIs are back transformed to provide geometric means. To assess whether an adjuvant is required in the formulation to enhance immune responses to IVX-A12, pairwise comparison of the GMT and GMFR least square means from this modeling between non-adjuvant and adjuvant groups will also be displayed. Also, to assess an improvement between the active treatments (IVX-A12a and IVX-A12d) versus placebo, pairwise comparison of the GMT and GMFR least square means from this modeling between IVX-A12a and Placebo and IVX-A12d and Placebo will be displayed. No adjustments for multiplicity will be performed. Data displays will also include boxplots of titers for anti-RSV/A-, RSV/B-, hMPV/A-, and hMPV/B specific NAb ([live-virus assays]) and RSV and hMPV IgG prefusion F protein-specific antibody titers ([ELISAs] at Day 28 for all ages. Log2 transformed titers will be used to create boxplots and back-transformed. The y-axis will be on a log scale. For anti-RSV/A- and RSV/B, the y-axis will display both sets of units.

The above analysis will be repeated as follows:

- By age subgroup analyses category. When using an ANCOVA, the outcome variable is Day 28 log2 transformed titers. The factors will include vaccine group, age stratification category and gender and the covariate is log2 transformed baseline titers;

This document is confidential.

- By baseline tertile; When using an ANOVA, the outcome variable is Day 28 log2 transformed titers. The factors will include vaccine group, age stratification category and gender;
- By age subgroup analyses category and baseline tertile. When using the ANOVA, the factors will include vaccine group, age stratification category, and gender.

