5.1.1.2. Co-primary Endpoints (Immunogenicity)

- Geometric mean titers (GMT) of RSV/A-, RSV/B-, hMPV/A-, and hMPV/B-specific NAb at Day 28;
- GMT of RSV and hMPV prefusion F protein-specific IgG antibody titers at Day 28;
- Proportion of subjects with a ≥ 4 -fold increase in serum anti-RSV/A-, RSV/B-, hMPV/A-, and hMPV/B-specific NAb from prevaccination/baseline (Day 0) to Day 28 after vaccination (defined as SRR);
- Proportion of subjects with ≥ 4 -fold increase (SRR) in RSV- and hMPV-specific IgG antibody titers from prevaccination/baseline (Day 0) to Day 28;
- Geometric mean fold rise (GMFR) at Day 28 versus Day 0 in serum anti-RSV/A-, RSV/B-, hMPV/A-, and hMPV/B-specific NAb and RSV and hMPV prefusion F protein-specific IgG antibody titers.

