7.1.2. Geometric Mean Fold Rise (GMFR)

Unadjusted and adjusted GMFRs will be calculated similarly as the unadjusted and adjusted GMTs.

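### SAP 9.1.1.1 names the Day 28 titer as the outcome for the adjusted GMFR; once that is corrected, the ANCOVA comparisons of GMFR repeat those of GMT apart from LLOQ handling

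*SAP*

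**What the plan says.** SAP 5.1.1.2 lists as a co-primary immunogenicity endpoint "Geometric mean fold rise (GMFR) at Day 28 versus Day 0", and SAP 7.2 defines fold change as the post-baseline value divided by the baseline value.

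SAP 9.1.1.1 builds the unadjusted GMFR on that scale: its interval comes from the "mean of the log2 transformed individual fold rise computed using Student's t distribution".

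For the adjusted analysis by ANCOVA, the same section gives one outcome for both statistics: "adjusted GMTs and GMFRs at Day 28 and its 95% CI will be calculated. The outcome variable is Day 28 log2 transformed titers". On the right-hand side, "The factors will include vaccine group, age stratification category, and gender" and "the covariates will include, log2 transformed baseline titers". Pairwise comparisons of both the GMT and the GMFR least squares means are then requested from this model: IVX-A12a against IVX-A12d to judge the need for adjuvant, and each of them against placebo. No multiplicity adjustment is made. The repeats by age subgroup (ANCOVA) and by baseline tertile (ANOVA without the baseline covariate) name the Day 28 titer again.

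SAP 9.1.2 sends the Day 180 and Day 365 adjusted GMFRs back to 9.1.1.1. SAP 7.1.2 adds only this: "Unadjusted and adjusted GMFRs will be calculated similarly as the unadjusted and adjusted GMTs". Protocol 13.1.3 mentions the ANCOVA for the adjusted GMT alone.

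**The concern.** A model for the log2 Day 28 titer gives, after back-transformation, a geometric mean titer. Read as written, the SAP asks for an adjusted GMFR and describes how to obtain a second copy of the adjusted GMT. The outcome is stated three times, so this is not a single slip, and the later visits inherit it.

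Correcting the outcome exposes a second matter. With log2 baseline already in the model, GMT and GMFR are no longer two comparisons. At Day 28 there are 6 assays × 3 pairs = 18 GMT ratios and 18 GMFR ratios. Anyone using them to judge the need for adjuvant could take agreement between the two sets as two findings, although it follows from the algebra.

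**Working it through.** **The plan's own figure.** SAP 4.3.1 claims more than 90% power for a 2-fold difference in GMT or GMFR, with SD 0.5 log10 and two-sided 0.05. Power = Φ(log10 2 / (SD × √(1/n1 + 1/n2)) − 1.96).

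- 100 v 100: 0.30103 / (0.5 × √0.02) = 4.257, power 98.9%.
- 100 v 50: 0.30103 / (0.5 × √0.03) = 3.476, power 93.5%.

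The noncentral t gives 98.9% and 93.2%. The claim is reproduced. It uses one SD for both endpoints and is unaffected by what follows.

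**Algebra.** Let Y be the log2 Day 28 titer, B the log2 baseline and F = Y − B the log2 fold rise. If Y = group + age + gender + βB + error, then F = group + age + gender + (β − 1)B + error. Only the baseline slope changes. Group coefficients, residuals, standard errors and p-values stay the same. Each least squares mean shifts by the constant mean(B), so adjusted GMFR = adjusted GMT / overall baseline geometric mean.

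**Numerical check.** This uses one simulated trial of 100/100/50 with the SAP's factors and SD 0.5 log10. Assumptions that are not in the documents: baseline centred on 2^10 = 1024, baseline slope 0.6, and mean log2 rises of 2.0 (IVX-A12a), 2.2 (IVX-A12d) and 0 (placebo).

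| Quantity | Outcome Y (as written) | Outcome F |
|---|---|---|
| IVX-A12a least squares mean, back-transformed | 3611.9 | 3.414 |
| Baseline slope | 0.662 | −0.338 |
| A12a/placebo (SE, log2) | 4.739 (0.259) | 4.739 (0.259) |
| A12d/placebo (SE, log2) | 5.598 (0.256) | 5.598 (0.256) |
| A12d/A12a (SE, log2; p) | 1.181 (0.210; 0.2524) | 1.181 (0.210; 0.2524) |

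The sample baseline geometric mean is 1058.06, and 3611.9 / 1058.06 = 3.414. Over 400 simulated trials the largest difference between the two contrasts was 2e-13 log2, which is rounding.

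**LLOQ rule (SAP 7.1).** When only the baseline is below LLOQ, the fold-rise denominator is LLOQ, whereas geometric means use half LLOQ. If the covariate also takes half LLOQ (an assumption), F is then 1 log2 unit lower than Y − B for that subject and the identity fails. The share of such baselines is not given, so a range is shown (GMT ratio v GMFR ratio):

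| Baselines below LLOQ (assumed) | A12a/placebo | A12d/placebo | A12d/A12a |
|---|---|---|---|
| 2% | 4.796 v 4.748 | 5.651 v 5.667 | 1.178 v 1.194 |
| 5% | 4.597 v 4.629 | 5.445 v 5.438 | 1.185 v 1.175 |
| 10% | 4.485 v 4.571 | 5.428 v 5.343 | 1.210 v 1.169 |
| 20% | 4.598 v 4.435 | 5.395 v 5.133 | 1.173 v 1.157 |

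The largest gap is 5.395 / 5.133 = 1.051.

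**Tertile ANOVA.** Without B in the model, the Y contrast minus the F contrast equals the difference in baseline between the arms within the tertile. In the simulated trial the lowest-tertile A12a/placebo ratio is 3.28 from Y and 4.06 from F. Over 400 trials (correlation 0.6) the mean absolute A12a/A12d difference was 0.172, 0.080 and 0.176 log2 in tertiles 1 to 3. The signed mean, over 1,500 trials at each of the correlations 0.3, 0.6 and 0.9, was never more than 0.011 log2 from zero. At correlation 0.6 each contrast's own SE is about 0.34 to 0.35, so the typical gap in the outer tertiles is about half an SE.

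**The case against.** The case for leaving the text alone has three parts. First, the intent is plain: the SAP defines fold change, says GMFRs are handled like GMTs, and asks for two sets of least squares means. SAP 15 also leaves table detail to mock shells that are not public. Second, because the models are equivalent, the titer ANCOVA already contains the adjusted GMFR, once the mean log2 baseline is subtracted. Third, SAP 7.1 states that no formal hypotheses are tested, so printing a ratio twice is a matter of presentation.

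The first part explains what a programmer would probably do, but it does not repair the text. SAP 7.1.2 names no outcome, the GMT section to which it points specifies titers, and the more specific section then states the titer. The second part is correct, but the SAP nowhere calls for the subtraction, and it gives no fold-rise contrast in the tertile ANOVA. The third part stands and limits the weight of the point.

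A reader might also infer more than the documents support:

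- **That the co-primary GMFR is wrong or lost.** It is not. Its unadjusted estimate and interval rest on individual fold rise, and no passage makes the adjusted version co-primary.
- **That GMT and GMFR comparisons always coincide.** They do so only with baseline as covariate and the same baseline value in both.
- **That the tertile results are biased.** The gap is chance imbalance in baseline, with expectation near zero under randomization.
- **That results would be wrong a thousandfold.** That needs a titer to be labelled as a fold rise, and the factor is simply the assumed baseline level.

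**Conclusion.** The point holds as an error in a stated rule, with modest consequences. By its literal text SAP 9.1.1.1 does not yield an adjusted GMFR in the main ANCOVA, the age-subgroup ANCOVA or the tertile ANOVA, and SAP 9.1.2 carries this to Days 180 and 365.

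After correction, the 18 Day 28 ANCOVA ratios for GMFR add nothing to the 18 for GMT. The equality is exact when the fold rise and the covariate use the same baseline value. It is approximate (within about 5% in the simulated range) when some baselines fall under the LLOQ rule. The exact part is algebra and needs no assumption about the data; the size of the LLOQ departure rests on the assumed 2% to 20% and on one simulated data set. In the tertile ANOVA the choice of outcome does change the contrast, by noise and not by bias. Power and error rates are untouched.

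**What to change.** In SAP 9.1.1.1, and in 9.1.2 which refers to it, state that the outcome for the adjusted GMFR is log2(Day X titer / Day 0 titer) in the ANCOVA, the age-subgroup ANCOVA and the tertile ANOVA. State also which LLOQ substitution the baseline covariate uses.

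For the ANCOVA pairwise comparisons, choose one of two displays. Either show the adjusted ratio once, with the adjusted GMFR given by group only, or keep both with a footnote that they are the same result apart from LLOQ handling and are not independent support. A footnote claiming exact equality would be inexact under the SAP's own LLOQ rule.

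The cost is a few lines of SAP text, one model statement and possibly fewer table rows; no new data are needed. The Protocol synopsis says that the Day 28 interim analysis has been performed, so it is also worth confirming which outcome the existing programs used.
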